4.1.1. Single-Ascending Dose Design

The study will comprise up to 4 dose cohorts.

Planned dosing information is provided in Section 6.1.

Dose escalation criteria are provided in Section 6.6.1.

Temporary stopping criteria are provided in Section 6.6.2

Cohorts 1 - 3 will comprise at least 8 participants:

- 6 randomized to LY3819253 and
- 2 randomized to placebo.

Sentinel dosing will be used in any dose cohort that represents a dose increase from the preceding cohort. The first 2 participants in each cohort will be randomized 1:1 to LY3819253 and placebo.

Safety and tolerability will be reviewed for sentinel participants up to 24 hours after dosing. The investigator and the Lilly sponsor team are responsible for determining if safety and tolerability is acceptable to continue with dosing subsequent participants.

Subsequent participants will be randomized to the remaining treatment allocations, 5 to LY3819253 and 1 to placebo.

The decision to dose the next cohort will be made when all participants from the previous cohort have been dosed and safety data is assessed for at least 4 days after the IV infusion by the investigator(s) and Lilly sponsor team.

Cohort 4 may be initiated, at the discretion of the sponsor team, if more data is needed to inform the dose of LY3819253.

4.2. Scientific Rationale for Study Design

This study is the first investigation of LY3819253 in humans. The study is designed to explore a range of doses that will inform the clinical drug development plan for LY3819253.

The sequential cohort, single-dose escalation design with safety reviews before each cohort will minimize safety risks to participants during dose exploration. Sentinel dosing is included to minimize the risk of any unanticipated acute tolerability or safety concerns in participants administered LY3819253.

The 4-day safety review after dosing is sufficient to monitor for an acute adverse immune response to treatment with LY3819253.

The optional, expansion Cohort 4 allows for additional data collection to detect reduction in the rate of clinical worsening.

In accordance with FDA recommendation (20 March 2020 Pre-IND Meeting), the population for this study are hospitalized patients infected with SARS-CoV-2.

Participants enrolling to this study will have moderate to severe COVID-19 illness according to the Food and Drug Administration (FDA) definitions (FDA resource page [WWW]), but with notable exception in the specific eligibility criterion #21 for severe participants. This exception is intended to limit the severity of the participant enrolling to this study to exclude those at highest risk of respiratory failure. Lilly believes the optimal benefit:risk for LY3819253 may be found in a participant that does not have impending respiratory failure, as this severity of patients with COVID-19 have primary pathology associated with overexuberant inflammatory response where LY3819253 is less likely to be effective. Further, adverse events in this population could potentially confound our ability to discern safety signals in this study.

Remote follow-up visits may be conducted to remove the burden of return visits for the hospital and clinical trial staff reflecting limited medical resources in the COVID-19 pandemic.

4.3. Justification for Dose

The dose levels selected for this study are designed to explore a wide exposure-response range that potentially encompasses a therapeutic dose, and will provide the safety and tolerability underpinnings for the clinical drug development plan for LY3819253.

Up to 4 cohorts will be enrolled to characterize the dose response of LY3819253 on safety, tolerability, PK and PD markers. The first 3 cohorts will explore the efficacious dose range (2 doses) and 1 supratherapeutic dose. The planned dose levels for LY3819253 are 700 mg, 2800 mg and 7000 mg.

Cohort 4 is optional and may be used to characterize the dose-response relationship for dose selection in subsequent studies. The dose for Cohort 4 may be evaluated at a lower or equal level to the maximum investigated dose but will not exceed 7000 mg.

The doses are determined based on these key variables:

- projected human PK of the mAb, including lung tissue distribution
- in vitro binding potency to the viral targets
- neutralization of virus cell entry and replication, and
- antibody-viral dynamic modeling and simulation.

The projected human half-life is expected to be approximately 19 days based on PK/PD modeling.

The starting dose of 700 mg is expected to have a sustained concentration above the *in vitro* IC90 of viral cell-entry neutralization for at least 28 days. The maximum dose of 7000 mg is selected due to uncertainty in model predicted PK concentrations, viral load reduction and consideration of infusion volume in participants.

The dose levels are fixed, not body weight based. Given the planned dose levels, the predicted impact of body weight on therapeutic response will be minimal.

4.4. End of Study Definition

A participant is considered to have completed the study if they have completed all required phases of the study including the last scheduled procedure shown in the SoA.

The end of the study is defined as the date of the last scheduled procedure shown in the SoA for the last participant.

5. Study Population

Prospective approval of protocol deviations to recruitment and enrollment criteria, also known as protocol waivers or exemptions, is not permitted. Due to the criticality of participant health and the setting of this research study, verbal interview of a potential participant, their legal representative or family member, may be the source for preexisting conditions and medical history unless otherwise specified within the eligibility criteria.

5.1. Inclusion Criteria

Participants are eligible to be included in the study only if all of the following criteria apply:

Age

1. Are ≥ 18 and ≤ 85 years of age at the time of randomization

Type of Participant and Disease Characteristics

- 2. In the judgement of the investigator, have moderate or severe COVID-19 illness per the FDA resource page (WWW) (Section 10.8, Appendix 8)
- 3. This criterion was removed
- 4. Are hospitalized, or in the process of being admitted to hospital, and have an initial laboratory determination of current COVID-19 infection ≤14 days of randomization.

Sex

- Are men or non-pregnant women Reproductive and Contraceptive agreements and guidance is provided in Section 10.4, Appendix 4.
- 6. Criterion 6 merged with criterion 5.

Study Procedures

- 7. Understand and agree to comply with planned study procedures
- 8. Agree to the collection of nasopharyngeal swabs and venous blood

Informed Consent

9. The participant or legally authorized representative give signed informed consent as described in Section 10.1.3, which includes compliance with the requirements and restrictions listed in the informed consent form (ICF) and in this protocol.

5.2. Exclusion Criteria

Participants are excluded from the study if any of the following criteria apply:

Medical Conditions

- 10. Require invasive mechanical ventilation or anticipated impending need for invasive mechanical ventilation
- 11. Anticipate transfer to another hospital which is not a study site within 5 days of randomization

- 12. Have known allergies to any of the components used in the formulation of the interventions
- 13. Have hemodynamic instability requiring use of pressors within 24 hours of randomization
- 14. Were resident in a nursing home or long-term care facility immediately prior to current hospitalization
- 15. Suspected or proven serious, active bacterial, fungal, viral, or other infection (besides COVID-19) that in the opinion of the investigator could constitute a risk when taking intervention
- 16. Have any co-morbidity requiring surgery within <7 days, or that is considered life-threatening within 29 days
- 17. Have prior history of hepatic impairment, such as
 - a. severe liver cirrhosis Child-Pugh B or worse
 - b. cirrhosis with a history of hepatic encephalopathy
 - c. clinically meaningful ascites requiring ongoing treatment with diuretics and/or paracentesis, or
 - d. history of hepatorenal syndrome.
- 18. Have any serious concomitant systemic disorder that, in the opinion of the investigator, would preclude participation in the study
- 19. Current diagnosis of active malignancy that, in the opinion of the investigator, could constitute a risk when taking investigational product
- 20. Received convalescent COVID-19 plasma treatment prior to enrollment

Diagnostic assessments

- 21. Have an SpO2 <88% while breathing room air at rest. If on supplemental oxygen at the time of screening, use the last time point of measurement on room air up to 48 hours prior
- 22. This criterion was removed
- 23. Have alanine aminotransferase (ALT) or aspartate aminotransferase (AST) >5X upper limit of normal (ULN)
- 24. Have acute kidney disease with an eGFR <30 mL/min/1.73 m² based on the chronic kidney disease epidemiology collaboration equation (CKD-EPI). Chronic kidney disease is allowable, if judged to be stable for the past 3 months, in the opinion of the investigator.

Other Exclusions

- 25. Are pregnant or breast feeding
- 26. Are concurrently enrolled in any other type of medical research judged not to be scientifically or medically compatible with this study
- 27. Are Lilly employees
- 28. Are investigator site personnel directly affiliated with this study or their immediate families.

5.3. Lifestyle Considerations

Reproductive and Contraceptive guidance is provided in Section 10.4, Appendix 4.

5.4. Screen Failures

Screen failures are defined as participants who consent to participate in the clinical study but are not subsequently enrolled in the study.

Repeating laboratory tests during the screening period does not constitute rescreening.

Individuals who do not meet the criteria for participation in this study (screen failure) may not be rescreened.

6. Study Intervention

Study intervention is defined as any investigational intervention(s), marketed product(s), placebo, or medical device(s) intended to be administered to/used by a study participant according to the study protocol.

6.1. Study Intervention(s) Administered

This is a single dose study.

Intervention Names	LY3819253	Placebo
Туре	Biologic	Not applicable
Dose Formulation	solution	0.9% Sodium chloride solution
Unit Dose Strength(s)	700 mg/vial	Placebo
Planned Dosage Level(s)	Cohort 1: 700 mg Cohort 2: 2800 mg Cohort 3: 7000 mg Optional Cohort 4 may explore lower or equal levels to the max investigated dose, but will not exceed 7000 mg.	Not applicable
Route of Administration	IV infusion	IV infusion
Use	experimental	placebo
IMP and NIMP	IMP	IMP
Sourcing	From Lilly	Commercially available 0.9% sodium chloride solution will be used as a placebo for this study
Packaging and Labeling	Study Intervention will be provided in glass vials and will be labeled appropriately	Commercially available 0.9% sodium chloride solution will be used as a placebo for this study

Abbreviations: IMP = investigational medicinal product; NIMP = non-investigational medicinal product.

This table describes the infusion volume and rate for the planned LY3819253 doses. Cohort 4 instructions will be provided in the pharmacy instructions. Placebo volume and rate will match the LY3819253 dose cohort.

LY3819253 Dose (mg)	Volume (mL)	Start Infusion rate x Time
700	50	100 mL/hr x 30 min
2800	75	100 mL/hr x 45 min
7000	100	100 mL/hr x 60 min

The infusion rate may be reduced as deemed necessary if an infusion reaction is observed.

During the infusion, vital signs will be monitored every 15 minutes as described in the SoA.

After completion of the infusion, participants will be monitored every 30 minutes for 2 hours and then every 1 hour for the next 4 hours.

The site must have resuscitation equipment, emergency drugs and appropriately training staff available during the infusion and for at least 4 hours after the completion of the infusion.

6.1.1. Special Treatment Considerations

6.1.1.1. Premedication for Infusions

Premedication for infusions is not planned. However, if an infusion reaction occurs during administration or if the participant has a medical history suggesting a potential benefit from premedication, the study investigator(s) should determine the appropriate premedication.

The investigators and sponsor may decide to use premedication for other cohorts if the frequency of infusion reactions among participants warrants it.

If minor infusion reactions are observed, but review of the data suggests that dose escalation may continue, administration of acetaminophen, 500 mg to 1000 mg, antihistamines and/or other appropriately indicated medications may be given prior to the start of infusions for subsequent participants.

The decision to implement premedication for infusions in subsequent cohorts will be made by the investigator and sponsor and recorded in the study documentation, along with the dose-escalation decision.

Any premedications given will be documented as a concomitant therapy.

6.1.1.2. Management of Infusion Reactions

All participants should be monitored closely, as there is a risk of infusion reaction and hypersensitivity (including anaphylaxis) with any biological agent.

Symptoms and Signs

Symptoms and signs that may occur as part of an infusion reaction include, but are not limited to fever, chills, nausea, headache, bronchospasm, hypotension, angioedema, throat irritation, rash including urticaria, pruritus, myalgia, and dizziness.

Infusion-related reactions severity will be assessed and reported using the Division of Allergy and Infectious Diseases (DAIDS) Table for Grading the Severity of Adult and Pediatric Adverse Events, version 2.1 (July 2017).

Parameter	Mild	Moderate	Severe	Severe and
				Potentially Life-threatening
Acute Allergic Reaction	Localized urticaria (wheals) with no medical intervention indicated	Localized urticaria with intervention indicated	Generalized Urticaria OR Angioedema with intervention indicated	Acute anaphylaxis OR Life-threatening bronchospasm
	Indicated	Mild angioedema with no intervention indicated	OR Symptoms of mild bronchospasm	OR Laryngeal edema
Cytokine Release Syndrome ^a	Mild signs and symptoms AND Therapy, that is, antibody infusion interruption not indicated	Therapy indicated (that is, antibody infusion) interruption indicated AND Responds promptly to symptomatic treatment OR Prophylactic medications indicated	Prolonged severe signs and symptoms OR Recurrence of symptoms following initial improvement	Life-threatening consequences (for example, requiring pressor or ventilator support)

This table describes the severity of reactions according to DAIDS.

^a = A disorder characterized by nausea, headache, tachycardia, hypotension, rash, and/or shortness of breath.

Source: Division of AIDS (DAIDS) Table for Grading the Severity of Adult and Pediatric Adverse Events, Version 2.1 (July 2017).

Site Needs

The clinical site should have necessary equipment and medications for the management of any infusion reaction, which may include but is not limited to oxygen, IV fluid, epinephrine, acetaminophen and antihistamine.

Management of Infusion Reactions

Investigators should determine the severity of the infusion reaction and manage infusion reactions based on standard of care and their clinical judgment. If an infusion reaction occurs, then supportive care should be used in accordance with the signs and symptoms.

If a participant permanently discontinues from study intervention, they should complete adverse event (AE) monitoring and other procedures as stated in the SoA.

6.1.1.3. In the Event of a Retrospective Positive Sterility Finding from Prepared Study Intervention

If a positive sterility finding occurs in the terminally sterile filtered study intervention, the participants who were dosed from the impacted batch should be contacted immediately and undergo a full physical examination including, but not limited to, blood pressure, pulse rate and body temperature.

A blood sample should be collected for culture and assayed for inflammatory markers such as C-reactive protein and elevations in white blood cell counts.

If the signs and symptoms indicated a participant has a possible infection, they will be clinically managed, treated and followed up until resolution. Any adverse events will be recorded as appropriate.

6.2. Preparation/Handling/Storage/Accountability

The investigator or designee must confirm appropriate temperature conditions have been maintained during transit for all study intervention received and any discrepancies are reported and resolved before use of the study intervention.

To protect blinding, the interventions must be prepared by an unblinded site personnel qualified to prepare study intervention who are not involved in any other study-related procedures. Instructions for preparation will be provided by the sponsor.

Only participants enrolled in the study may receive study intervention and only authorized site staff may supply or administer study intervention.

All study intervention must be stored in a secure, environmentally controlled, and monitored (manual or automated) area in accordance with the labeled storage conditions with access limited to the investigator and authorized site staff.

The investigator, institution, or the head of the medical institution (where applicable) is responsible for study intervention accountability, reconciliation, and record maintenance (i.e., receipt, reconciliation, and final disposition records).

Further guidance and information for the final disposition of unused study interventions are provided in the pharmacy manual.

6.3. Measures to Minimize Bias: Randomization and Blinding

This is a blinded study.

All participants will be centrally randomized to study intervention using an Interactive Web Response System (IWRS). Before the study is initiated, the log in information and directions for the IWRS will be provided to each site.

This table describes general procedures for unblinding.

Unblinding (IWRS)	• Emergency unblinding for adverse events may be performed through the
	IWRS. All actions resulting in an unblinding event are recorded and
	reported by the IWRS
	• In case of an emergency, the investigator has the sole responsibility for
	determining if unblinding of a participants' intervention assignment
	is warranted
	• Participant safety must always be the first consideration in making such a
	determination. However, the investigator should make all attempts to
	contact the sponsor in advance of unblinding
	• If a participant's intervention assignment is unblinded, the sponsor must be
	notified immediately after breaking the blind even if consultation occurred
	in advance
	• The date and reason that the blind was broken must be recorded in the
	source documentation and case report form

Abbreviations: IWRS = interactive web-response system.

If an investigator, site personnel performing assessments, or participant is unblinded while the infusion is ongoing, the participant must be discontinued from the study intervention and the infusion stopped. If any amount of study intervention was administered, follow procedures according to the SoA as described in Section 7.1.

6.4. Study Intervention Compliance

Participants will receive study intervention directly from the investigator or designee, under medical supervision. The date and time of each dose administered will be recorded in the source documents and recorded in the case report form (CRF).

6.5. Concomitant Therapy

Prior Treatment for Indication

Any prior therapy, such as antivirals, antibiotics, or antimalarials used as treatment prior to signing informed consent should be recorded.

Therapy prior to enrollment with antivirals including lopinavir/ritonavir, remdesivir or other therapeutic agents (e.g. corticosteroids) are permitted.

Convalescent COVID-19 plasma treatment is not allowed prior to enrollment.

Concomitant Therapy

Participants should be treated according to standard of care, even as it evolves, and medications may be part of the treatment paradigm. Therefore, remdesivir may be initiated as standard of care for participants hospitalized with severe disease (if available through the FDA Emergency Use Authorizations) outside of local standard of care per written policies or guidelines.

If the local standard of care per written policies or guidelines (that is, not just an individual clinician decision) includes lopinavir/ritonavir, chloroquine, hydroxychloroquine or other investigational agents, then initiating these during the study is permitted, but may require additional safety monitoring by the site.

Convalescent COVID-19 plasma treatment is not allowed.

Any medication, investigational agent, or vaccine, including over the counter or prescription medicines, vitamins, and/or herbal supplements, or other specific categories of interest that the participant is receiving at the time of enrollment or receives during the study must be recorded along with:

- Reason for use
- Dates of administration including start and end dates
- Dosage information including dose and frequency for concomitant therapy of special interest

Acetaminophen and corticosteroid use are permitted at any time during the study.

Other concomitant medication may be considered on a case-by-case basis by the investigator in consultation with the sponsor if required.

The sponsor should be contacted if there are any questions regarding concomitant or prior therapy.

6.6. Dose Modification

6.6.1. Dose Escalation Criteria

By nature of being a Phase 1 sponsor unblinded dose-escalation study, data will be evaluated on an ongoing basis until the highest planned dose has been administered.

The decision to dose the next cohort will be made when all participants from the previous cohort have been dosed and safety data, including safety laboratory data, AEs and vital signs, are assessed for at least 4 days after the IV infusion by the investigator(s), Lilly sponsor team and an independent safety assessment committee (ISAC).

The investigator, Lilly sponsor team and ISAC are responsible for determining any dose decisions. The investigator(s) will remain blinded and the Lilly sponsor team and ISAC will be unblinded during these reviews. All available data from previous cohorts will be reviewed. Available PK and PD data may also be used to guide dose adjustment.

If temporary stopping criteria are met (Section 6.6.2), dosing will be temporarily stopped and no further participants will be dosed until a full safety review of the study has taken place. The ISAC will be engaged for the full safety review with the sponsor and investigator.

6.6.2. Temporary Stopping Criteria

Dosing will be temporarily halted, and no further participants will be dosed until a full safety review of the study has taken place if:

 Two or more participants at a given dose level develop severe or severe/potentially lifethreatening acute AEs related to the infusion (see Table in Section 6.1.1.2), during or within 2 hour of completion of the infusion, that do not resolve with a reduced infusion rate and/or supportive care.

OR

• Two or more participants at a given dose level develop severe acute AEs within 4 days of dosing which, in the opinion of the investigator, cannot be attributed to the primary disease, concomitant medications or extraneous circumstances with a reasonable possibility.

This table describes the location of AE-related information in this protocol.

Торіс	Location
DAIDS table describing severity of reactions	Section 6.1.1.2
Definition of AEs	Section 10.3.1
Assessment of Intensity/Severity	Section 10.3.3

Changes to the planned dosing schedule must be appropriately documented and communicated with the study personnel and the IRB/IEC before dosing continues.

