10.3.3. Recording and Follow-Up of AE and/or SAE

AE and SAE Recording

When an AE/SAE occurs, it is the responsibility of the investigator to review all documentation (e.g., hospital progress notes, laboratory reports, and diagnostics reports) related to the event.

The investigator will then record all relevant AE/SAE information in the CRF.

It is **not** acceptable for the investigator to send photocopies of the participant's medical records to Sponsor or designee in lieu of completion of the AE/SAE CRF page.

There may be instances when copies of medical records for certain cases are requested by Sponsor or designee. In this case, all participant identifiers, except the participant number, will be redacted on the copies of the medical records before submission to Sponsor or designee.

The investigator will attempt to establish a diagnosis of the event based on signs, symptoms, and/or other clinical information. Whenever possible, the diagnosis (not the individual signs/symptoms) will be documented as the AE/SAE.

Assessment of Intensity/Severity

The investigator will make an assessment of intensity for each AE and SAE reported during the study and assign it to one of the following categories, which together with serious criteria on the AE CRF ("results in death" and "life-threatening"), are aligned with the Division of AIDS (DAIDS) Table for Grading the Severity of Adult and Pediatric Adverse Events, version 2.1 (July 2017).

Mild: Mild symptoms causing no or minimal interference with usual social and functional activities, with intervention not indicated.

Moderate: Moderate symptoms causing greater than minimal interference with usual social and functional activities, with intervention indicated.

Severe: Severe symptoms causing inability to perform usual social and functional activities, with intervention or hospitalization indicated.

An event is defined as 'serious' when it meets at least 1 of the predefined outcomes as described in the definition of an SAE, NOT when it is rated as severe.

Assessment of Causality

The investigator is obligated to assess the relationship between study intervention and each occurrence of each AE/SAE.

A "reasonable possibility" of a relationship conveys that there are facts, evidence, and/or arguments to suggest a causal relationship, rather than a relationship cannot be ruled out.

The investigator will use clinical judgment to determine the relationship.

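### Two life-threatening infusion reactions at one dose that recover, and that also have another reasonable cause, can escape both pre-set halt criteria in Protocol 6.6.2

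*Protocol*

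**What the plan says.** Protocol 6.6.2 gives two criteria joined by OR. Either one stops dosing until a full safety review.

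- **Criterion 1** needs two or more participants at a dose level with severe or severe/potentially life-threatening acute events related to the infusion, occurring "during or within 2 hour of completion of the infusion, that do not resolve with a reduced infusion rate and/or supportive care".
- **Criterion 2** needs two or more participants at a dose level with severe acute events within 4 days of dosing which, in the investigator's opinion, "cannot be attributed to the primary disease, concomitant medications or extraneous circumstances with a reasonable possibility".

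Protocol 6.1.1.2 supplies the grading and the management advice. Top-grade cytokine release syndrome is described as "Life-threatening consequences (for example, requiring pressor or ventilator support". Sites are to hold equipment and medications for infusion reactions, "which may include but is not limited to oxygen, IV fluid, epinephrine, acetaminophen and antihistamine". If a reaction occurs, "then supportive care should be used in accordance with the signs and symptoms". No section says which treatments count as supportive care or where it ends.

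Protocol 4.1.1 plans 6 active and 2 placebo participants in each of Cohorts 1-3. One active and one placebo participant are dosed first as sentinels, then 5 active and 1 placebo.

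**The concern.** A reaction that needs a pressor is, by the protocol's own example, life-threatening. If the participant then recovers, a site may record it as resolved with supportive care, and criterion 1 does not count it. Nothing in criterion 1 makes an exception for the top grade.

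Criterion 2 is the backstop, but it depends on a blinded investigator's view of other causes. Participants have moderate or severe COVID-19, and Protocol 6.5 allows remdesivir and, where written local policy includes them, other agents. An event can be judged related to the infusion and also have a reasonable alternative cause. Such an event fails criterion 2.

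Protocol 2.3 names infusion-related hypersensitivity and cytokine release as the manageable risks of this first-in-human antibody. The other safeguards in the documents rest on judgment:

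- Sentinel review covers one active participant per cohort.
- The 4-day review follows dosing of the whole cohort and governs the next one.
- Serious events reach the sponsor within 24 hours, but no stated count then stops dosing.

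No minimum interval is given between the participants dosed after the sentinels.

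**Working it through.** **Logic check.** Take two top-grade infusion reactions at one dose, both starting within the 2-hour window and both recovering on a pressor. Read criterion 2's word severe as including the top grade.

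| Case | Criterion 1 | Criterion 2 | Halt? |
|---|---|---|---|
| Site treats a pressor as beyond supportive care | met | not needed | yes |
| Pressor counted as supportive; no other reasonable cause for either event | not met (resolved) | met | yes |
| Pressor counted as supportive; another reasonable cause for either event | not met (resolved) | not met (fewer than two count) | no |

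Only the last row is a gap. It needs both conditions.

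**How plausible is another cause?** The footnote in 6.1.1.2 describes cytokine release as "A disorder characterized by nausea, headache, tachycardia, hypotension, rash, and/or shortness of breath", which is six features. In the eligible moderate and severe categories, Appendix 8 (10.8) names headache, raised heart rate and shortness of breath: 3 of 6, or 4 of 6 if nausea is counted as a gastrointestinal symptom. Low blood pressure appears there only under Critical disease, and rash not at all.

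**The plan's own figure.** Protocol 9.2 claims more than 80% probability of observing an event of 25% prevalence among 6 participants: 1 − 0.75^6 = 0.822. This reproduces, but it concerns seeing at least one event. No operating characteristic is stated for the halt rule.

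**Illustrative size.** From the documents: n = 6 active, count of two or more. Assumed: every top-grade reaction resolves with care the site calls supportive; p is the true top-grade rate; a is the share with another reasonable cause; r is the share of those still judged infusion-related. Only top-grade reactions are modelled.

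- Current rule: each participant yields a countable event with probability q = p(1 − a), because criterion 1 contributes nothing.
- Changed rule: q = p(1 − a) + p·a·r.
- P(halt) = 1 − (1 − q)^6 − 6q(1 − q)^5.

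Worked case, p = 10%, a = 25%, r = 50%:

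- Current: q = 0.075, so 1 − 0.6264 − 0.3047 = 0.069.
- Changed: q = 0.075 + 0.0125 = 0.0875, so 1 − 0.5773 − 0.3321 = 0.091.

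| p | a | Current | Changed, r = 50% | Changed, r = 100% |
|---|---|---|---|---|
| 2% | 25% | 0.3% | 0.4% | 0.6% |
| 2% | 50% | 0.15% | 0.3% | 0.6% |
| 5% | 25% | 1.9% | 2.6% | 3.3% |
| 5% | 50% | 0.9% | 1.9% | 3.3% |
| 10% | 25% | 6.9% | 9.1% | 11.4% |
| 10% | 50% | 3.3% | 6.9% | 11.4% |
| 20% | 25% | 22.4% | 28.3% | 34.5% |
| 20% | 50% | 11.4% | 22.4% | 34.5% |

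At a = 0 or r = 0 the two rules agree.

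**Participants spared.** The rule acts after the second event, so at most 6 − 2 = 4 active participants can be spared. If participants are dosed one at a time and the halt is immediate, the expected number spared is the sum over m = 2 to 5 of P(at least two events in m). At p = 10%, a = 25%, r = 50% this is 0.100 currently and 0.134 after the change, a gain of about 0.03 per cohort.

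**Cohort 4.** With about 50 active, the chance of two or more events at a 2% rate is 1 − 0.98^50 − 50(0.02)(0.98^49) = 26%. For four or more it is 1.8% at 2%, 24% at 5% and 75% at 10%.

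**The case against.** The case for leaving the text alone is serious.

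- **Supportive care.** Epinephrine appears under site supplies, while supportive care is mentioned in a separate management paragraph, and no text equates them. Criterion 1 expressly includes life-threatening events, which has little effect if pressors count as supportive. This makes the exempting reading less natural. It does not exclude it, because the term is left undefined.
- **Attribution.** Onset within 2 hours of the infusion points away from COVID-19. Exclusion 13 removes people who "Have hemodynamic instability requiring use of pressors within 24 hours of randomization", and exclusion 10 removes those with impending need for invasive ventilation. Protocol 10.3.3 says that a reasonable possibility "conveys that there are facts, evidence, and/or arguments to suggest a causal relationship, rather than a relationship cannot be ruled out". That definition is written for causality of the study intervention, but the same standard is the natural one here. This stands: attributing such events to COVID-19 should be uncommon, so a = 50% is a favourable assumption.
- **Other oversight.** Protocol 6.6.1 has data evaluated on an ongoing basis by an unblinded sponsor, Section 8 requires immediate safety concerns to be raised with the sponsor at once, and 9.5 has the safety committee monitoring unblinded data throughout. This also stands. What is missing is only a numeric trigger within a cohort.

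Three stronger readings are tempting, and the documents do not support them. A reader might infer that recovered life-threatening reactions never stop dosing, but criterion 2 counts them when no other cause is reasonable. A reader might infer that 6.6.2 is the trial's only automatic stop, but 9.5 and 10.1.5 defer detail to a committee charter that is not among the documents. A reader might infer that all 5 active participants dosed after the sentinel are what a corrected rule would protect, but it can spare at most 4.

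**Conclusion.** The gap is real but narrow. As worded, 6.6.2 does not count a recovered top-grade infusion reaction that has another reasonable cause when the site regards its treatment as supportive. Two such reactions at one dose trigger no pre-set halt that these documents state.

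The illustrative gain at p = 10%, r = 50% is 2.2 percentage points if a quarter of events have another reasonable cause, and 3.6 points if half do. These figures rest on assumed rates and on every reaction resolving, and they would be smaller at lower a. Even with every event counted, a 10% rate halts a 6-participant arm only 11.4% of the time, so review by judgment remains the main protection. No figure in the plan is wrong. This is an inexpensive improvement to a safety rule, worth making because it concerns the most dangerous grade of a risk that the protocol itself names.

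**What to change.** For Cohorts 1-3, reword criterion 1 to count acute infusion-related events starting by 2 hours after the infusion ends that are either (a) severe/potentially life-threatening, whether or not they resolve, or (b) severe and not resolving with a slower infusion or supportive care. Two participants with (a), (b) or one of each meet the criterion. Leave criterion 2 as it is, since filtering out disease-attributed events there is defensible.

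State that counts are kept per cohort. Cohort 4 may repeat an earlier dose, and the criteria now count by dose level, so without this it could inherit an earlier count. Cohort 4 should keep the current criterion 1 or use a higher count of resolved top-grade events, such as four. A count of two there would pause dosing too readily.

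The cost is a short protocol edit and matching charter text, with no extra participants or procedures. The downside is an occasional extra temporary pause. With 6 active, and counting top-grade reactions alone, it is at most 0.6% per cohort at a true rate of 2% and 3.3% at 5%. If all 3 permitted additional participants were active (n = 9), the same formula gives 1.3% and 7.1%. Severe unresolved reactions combining with a top-grade one would add somewhat to these figures.
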